5 STUDY ASSESSMENTS AND PROCEDURES

5.1 Pre-Treatment Period

- During the Pre-Treatment Period, during which the participant will follow the schedule found in table 5-1, subjects are consented and qualified (screened) for the study. Informed consent must be obtained before initiation of any clinical screening procedure that is performed solely for the purpose of determining eligibility for this study. Evaluations performed as part of routine care before informed consent can be considered as screening evaluations if done within the defined screening period, and if permitted by the site's institutional review board (IRB)/ethics committee (EC) policies. Study eligibility is based on meeting all of the study inclusion criteria and none of the exclusion criteria at screening and on Study Day 1 before study treatment administration. The following assessments will be conducted before subjects receiving their first dose of cabozantinib on this protocol:

1. For patients with measurable visceral metastases CT scans with contrast or MRI including chest/abdomen/and pelvis are required.
2. Demographics
3. Medical and cancer history/demographics
4. Height
5. Weight
6. Vital Signs
7. ECOG Performance Status

Proprietary Information of MD Anderson

8. Clinical laboratory testing

- chemistry panel (albumin, alkaline phosphatase, ALT, AST, bicarbonate, blood urea nitrogen, calcium, chloride, creatinine, glucose, , magnesium, phosphorus, potassium, sodium, total bilirubin, total protein)
- hematology tests(CBC, differential, platelets)
- adrenal hormonal assessment
- urinalysis and UPCR
- thyroid function tests (TSH, free T4)
- pregnancy test (urine or serum) for women of child-bearing potential
- PT/INR, PTT
- Serum mitotane level if used mitotane within 6 months

9. ECGs

10. Physical examination, safety and adverse events evaluation will be performed at baseline.

For each subject, the Pre-Treatment Period ends upon receipt of the first dose of study treatment or final determination that the subject is ineligible for the study.

5.2 Treatment Period

During the Treatment Period subjects will receive cabozantinib until either disease progression, the occurrence of unacceptable drug-related toxicity or for other reason(s) for subject withdrawal as described in Section 2.5. Subjects should be instructed to immediately inform the principal investigator (PI) of any AEs. Subjects experiencing dizziness, sleepiness, or other symptoms that could influence alertness or coordination should be advised not to drive or operate other heavy machinery.

The following schedule of assessments applies to all subjects (Table 5-1). More frequent assessments should be obtained if clinically indicated.

Proprietary Information of MD Anderson

Table 5-1: Study Assessments

				Study Treatment Period			Post-Treatment Period
	Within 28 days before 1 st Dose of Study Treatment	Day 1	Day 1 of Weeks 3, 5, then every 4 weeks (± 5 days)	Day 1 of Week 5 (± 5 days)	Day 1 of Week 9 (± 5 days)	At Progression (+ 5 days)	30 - 37 Days after last dose
Informed consent	X						
Demographics	X						
Medical and cancer history/demographics	X						
Physical examination	X		X				X
Height	X						
Weight	X		X				X
Vital signs	X		X				X
ECOG performance status	X		X				X
Clinical laboratory tests ¹	X		X ²				X
Urinalysis and UPCR ¹⁰	X		X ²				X
PT/INR, PTT	X		X ¹²				
TFTs (TSH, free T4)	X		X ²				
12-lead ECG ⁸	X		X				X
Cabozantinib administration		X	X (daily)				
Pregnancy test	X	X ⁹	X ²				X
Tumor assessment ³	X		X (every 8 weeks)				
Adrenal hormonal profile ⁴	X		X (every 8 weeks)				
Serum mitotane level ⁵	X						
Concomitant medications	X	X	X				X
Adverse events	Continuous						X
Immunologic assessments ¹¹	X ¹¹				X ¹¹	X ¹¹	
Pharmacogenetic assessment ¹¹	X ¹¹						
Pharmacokinetic assessment ⁶		X ⁶		X ⁶			
Optional biopsy ⁷	X ⁷			X ⁷		X ⁷	

Proprietary Information of MD Anderson

ECG, electrocardiogram; ECOG, Eastern Cooperative Oncology Group; PT/INR, prothrombin time/International Normalized Ratio; PTT, partial prothrombin time, TFT, thyroid function test; UPCR, urine protein/urine creatinine ratio

¹Laboratory tests should include a standard hematology panel (CBC, differential, platelets) and chemistry panel (albumin, alkaline phosphatase, ALT, AST, bicarbonate, blood urea nitrogen, calcium, chloride, creatinine, glucose, , magnesium, phosphorus potassium, sodium, total bilirubin, total protein)

²Every 8 weeks (+/- 5 days) after the first 12 weeks

³All sites of known disease must be assessed with CT or MRI. In patients with IV contrast allergy or borderline renal function, CT without IV contrast or 18 FDG PET CT may be used as clinically indicated.

⁴ No additional measurements of adrenal hormones (ACTH, cortisol, aldosterone, plasma renin activity, DHEA-sulfate, testosterone in women, estradiol in men and postmenopausal women) are needed in patients with normal profile at baseline (Non-functioning ACC).

⁵ No need for mitotane measurement in patients who have been off mitotane for > 6 months or never received mitotane.

⁶Full pharmacokinetic assessment on day 1 and day 29(+/- 5 days) then one trough level every 12 weeks (+/- 6 weeks); On day 1 and 29 (+/- 5 days): PK blood samples (10 mL) are to be collected within 15 minutes prior to dosing of cabozantinib and at the following time points following ingestion of the dose: 1 hour (\pm 15 minutes), 2 hours (\pm 15 minutes), 4 hours (\pm 15 minutes), and 8 hours (\pm 15 minutes) post-dose.

⁷ Optional imaging guided biopsy from an accessible tumor site to be done at baseline, 29 days (+/- 5 days), and at time of progression.

⁸ If QTcF interval within normal range at baseline and subsequent ECGs at weeks 3 and 5, then no need for routine ECG monitoring. ECGs may be ordered as needed if there is other clinical indication.

⁹ Within 48 hours prior to day 1

¹⁰ Consider 24-hour urine collection for protein if UPCR>1mg/mg

¹¹ A 50 cc blood sample to be collected for immunologic testing at screening, at week 9 day 1(+/- 5 days), and at progression (+ 5 days). A 10 cc to be collected for pharmacogenetic screening at screening only.

¹² If abnormal at baseline or clinically indicated

If the subject is unable to have a study assessment taken within the defined time window due to an event outside of his or her control (e.g., clinic closure, personal emergency, inclement weather, vacation), the assessment should be performed as close as possible to the required schedule.

Regular tumor assessments should be performed in accordance to the guidelines in Section 5.5 to determine if PD is present.

The Treatment Period ends when a subject receives his or her last dose of study treatment; the subject then enters the Post-Treatment Period.

5.3 Post-Treatment Period

Subjects will return to the study site 30 to 37 days after their last dose of cabozantinib to complete end-of-study assessments.

Laboratory and physical examinations will be performed. Remaining study treatment will be returned by the subject, and treatment compliance will be documented. Additional follow-up will occur for subjects

Proprietary Information of MD Anderson

with AEs related to study treatment that are ongoing at the time of this visit, and for subjects with SAEs related to study treatment that occur after the time of this visit.

Proprietary Information of MD Anderson

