2.5 Withdrawals

Subjects may discontinue study treatment or withdraw their consent to participate in the study at any time without prejudice. The investigator may withdraw a subject from study treatment or from the study if, in his or her clinical judgment, it is in the best interest of the subject or if the subject cannot comply with the protocol.

In addition, any of the following conditions require discontinuation of the subject from study treatment:

- An AE or intercurrent illness that in the opinion of the investigator warrants the subject's withdrawal from study treatment;
- The investigator believes it is not in the best interest of the subject to continue on study
- Specific conditions described in the Management of Adverse Events Sections 3.3.2 and 3.3.2.1;
- Necessity for treatment with other anticancer treatment prohibited by protocol;
- Sexually active subjects who refuse to use medically accepted barrier methods of contraception (e.g, male condom, female condom) during the course of the study and for 4 months after discontinuation of study treatment;
- Women who become pregnant or are breastfeeding;
- If the subject does not recover from his or her toxicities to tolerable Grade ≤ 2 within 6 weeks, the subject will have study treatment discontinued unless there is unequivocal evidence that the subject is benefitting. In this situation, a subject may be able to restart therapy with a dose reduction upon resolution of the toxicity and with agreement of the principal investigator / MD Anderson IND Office;
- Request by regulatory agencies for termination of treatment of an individual subject or all subjects under the protocol;
- Significant noncompliance with the protocol schedule in the opinion of the investigator;
- The minimum dose of study treatment will be 20 mg once daily (qd). Subjects who cannot tolerate 20 mg qd will have study treatment discontinued;

Proprietary Information of MD Anderson

- Progressive disease (PD) or the subject no longer experiences clinical benefit as determined by the investigator

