5.5 Tumor Assessment

Serial imaging studies will be used to assess measurable disease per RECIST 1.1 criteria (9). Contrast-enhanced computerized tomography (CT) scan or magnetic resonance imaging (MRI) of chest/abdomen/pelvis will be obtained every 8 weeks (+/- 5 days) after the start of study drug administration. In patients with IV contrast allergy or borderline renal function, CT without IV contrast or 18 FDG PET CT may be used as clinically indicated.

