7.3 Sample Size

This is a pilot clinical trial and is not powered for significance in statistical comparison as there is insufficient existing evidence to predict the likely outcomes. The maximum number of subjects to be recruited for the study is 18.

It is expected for the current trial that the drug will achieve a minimum PFS4 of 20% while the maximum toxicity rate should be below 30%. PFS4 is defined as no disease progression or death within the first 4 months of the proposed treatment. If the trial is not terminated early, a posterior 90% credibility interval for the primary endpoint PFS4 rate will have a width of 0.271, given 3 patients achieving PFS4 under the assumption of 20% PFS4 rate.

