7.4 Safety and Futility Monitoring

The PFS4 and toxicity rates will be monitored simultaneously using the Bayesian approach of Thall, Simon, Estey (10) as extended by Thall and Sung (11), an effective and flexible method which has been successfully applied in hundreds of clinical trials at UT-MD Anderson and other institutions. The prior probabilities of PFS4 and toxicity for the experimental regimen are modeled by beta distributions (*Beta*(0.20, 0.80) and *Beta*(0.25 0.75), respectively). Denoting the probabilities of PFS4 and study drug-related toxicity rate of the experimental treatment by {p(PFS4,E) , p(TOX,E)}, the following decision criteria will be applied:

the trial will be stopped early either due to futility if

$$\text{Prob}\{ \text{p(PFS4,E)} < 0.20 \mid \text{data} \} > 0.90,$$

or due to toxicity if

$$\text{Prob}\{ \text{p(TOX,E)} > 0.25 \mid \text{data} \} > 0.90.$$

The above futility and toxicity monitoring rules will be implemented by a cohort size of 3, starting from the 6th enrolled patient. Patients will be monitored according to the stopping boundaries for PFS4 or study drug-related toxicity specified in **Table 7-1**. For example, the patient enrollment will be stopped if more than 3 severe toxicities (Grade 4) are observed among the first 6 patients. The patient enrollment will continue unless the stopping boundary is reached for evaluable subjects. The corresponding operating characteristics are listed in the **Table 7-2**.

Table 7-1: Stopping boundaries for PFS4 and study-related toxicity

Number of patients evaluated	Stop if # of PFS4 observed	Stop if # of toxicity observed
6	0	4-6

Proprietary Information of MD Anderson

9	0	5-9
12	0-1	6-12
15	0-1	7-15
18	Always stop with this many patients	

Table 7-2: Operating Characteristics (based on simulations from 10,000 trials)

True PFS4 Rate	True Toxicity Rate	Prob (stop the trial early)	Average number of patients treated
0.1	0.10	0.720	10.5
	0.30	0.774	9.9
	0.50	0.930	8.1
0.25	0.10	0.243	15.5
	0.30	0.387	14.2
	0.50	0.809	10.1
0.4	0.10	0.057	17.4
	0.30	0.237	15.9
	0.50	0.763	10.9

The above stopping boundaries were calculated using MultcLean (v.2.1.0) design software (<http://biostatistics.mdanderson.org/Software Download>).

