The Investigator is responsible for completing a Safety/Efficacy Summary Report, and submitting it to the IND Office Medical Affairs and Safety Group, for review and approval. This should be submitted after the first 6 evaluable patients per cohort, complete 4 months of study treatment, and every 3 evaluable patients per cohort, thereafter. On every summary submission, toxicity will be assessed after one month, and efficacy after four months of therapy.

A copy of the cohort summary should be placed in the Investigator's Regulatory Binder under "MD Anderson IND Office correspondence".

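### The interim looks are worded by completed drug treatment although PFS4 is event-based, and a patient who stops drug early without progression has no required scan to settle month-4 status

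*Combined protocol and SAP*

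**What the plan says.** **Endpoint.** Section 7.3: "PFS4 is defined as no disease progression or death within the first 4 months of the proposed treatment". The definition does not mention staying on drug. The same section gives a 90% credibility interval of width 0.271 for 3 patients achieving PFS4, with a maximum of 18 patients.

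**Who enters the looks.** The plan words this in four ways:
- Section 7.4, enrolled patients: "The above futility and toxicity monitoring rules will be implemented by a cohort size of 3, starting from the 6th enrolled patient".
- Section 7.4, evaluable patients: "The patient enrollment will continue unless the stopping boundary is reached for evaluable subjects". The term is not defined; section 7.1 defines only a safety population.
- Section 7.4, summary report: to be "submitted after the first 6 evaluable patients per cohort, complete 4 months of study treatment".
- Section 7.5: efficacy is reviewed once 6, 9, 12 and 15 patients have finished four months of cabozantinib. If too few PFS4 successes have been reached, enrolment is halted until there are enough.

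**When drug stops.** Section 2.5 lists among the reasons that require stopping treatment: "Progressive disease (PD) or the subject no longer experiences clinical benefit as determined by the investigator". It also lists reasons without progression, such as an adverse event, noncompliance or a need for other anticancer treatment. Section 2.5.1 gives replacements as not applicable.

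**Scans.** Section 5.5 says that CT or MRI "will be obtained every 8 weeks (+/- 5 days) after the start of study drug administration" and gives no end. Table 5-1 marks tumor assessment at screening and during treatment; its post-treatment cell is blank. Section 5.2: "The Treatment Period ends when a subject receives his or her last dose of study treatment; the subject then enters the Post-Treatment Period". Section 5.3 then has one visit: "Subjects will return to the study site 30 to 37 days after their last dose of cabozantinib to complete end-of-study assessments". It names laboratory tests and physical examination, not imaging.

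**The concern.** The Table 7-1 futility boundaries are 0 or 1 success, so the plan must say who is counted and what an unknown status means. It is unclear on both.

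First, progression requires stopping drug. Patients who have finished four months of drug are therefore almost all patients who have not progressed. Taken literally, that wording removes the failures from the count that is meant to detect failure.

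Second, a patient who stops for another reason before month 4 may have no later scan. Kaplan-Meier (section 7.5) can censor such a patient on a curve, but the look boundaries and the section 7.3 interval need a yes or a no. In an open-label trial of 18 patients, that decision would be made after the data are seen.

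**Working it through.** **1. The plan's interval.** Inputs: prior Beta(0.20, 0.80) from 7.4; 3 successes and at most 18 patients from 7.3. Posterior Beta(0.20 + 3, 0.80 + 15) = Beta(3.2, 15.8). Equal-tailed 90% interval 0.053 to 0.324, width 0.271, as stated. With 3/17 the width is 0.284 and with 3/16 it is 0.299. The stated figure therefore uses all 18 patients.

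**2. The plan's boundaries and operating characteristics.** The rule Pr(PFS4 < 0.20 | data) > 0.90 gives futility boundaries 0, 0, 0–1 and 0–1 at 6, 9, 12 and 15 patients, as in Table 7-1. Exact enumeration, with PFS4 and toxicity independent, reproduces all nine early-stop probabilities in Table 7-2 to three decimals (for example 0.243 at PFS4 0.25 and toxicity 0.10). It treats every patient's status as known.

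**3. Futility stopping alone.** A trial that passes the look at 6 has at least one success, so the look at 9 adds nothing. The look at 12 then stops only if there is one success in the first six and none in the next six; the look at 15 adds nothing further. Hence F(p) = (1 − p)^6 + 6p(1 − p)^11. At p = 0.20: 0.262 + 0.103 = 0.365.

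**4. Literal count of finishers.** If nearly everyone counted is a success, p is near 1 and F(p) is about 0. The rule could hardly stop the trial at any true PFS4.

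**5. What one status can change.**
- Look at 6: 0/6 gives 0.972 (stop); 1/6 gives 0.658 (continue).
- Look at 12: 1/12 gives 0.901 (stop); dropping one failure, 1/11 gives 0.878 (not above 0.90); 2/12 gives 0.671 (continue).
- Enrolment halt in 7.5: suppose one of the first six statuses is unknown. The unknown matters only if none of the other five is a success. The probability is 0.80^5 = 0.33 at a true 20%, or 0.75^5 = 0.24 at 25%.

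**6. Timing.** Four months is 4 × 30.4375 = about day 122. The week-16 scan falls on day 112 ± 5. The post-treatment visit comes 30 to 37 days after the last dose, so a patient whose last dose is before about day 85 to 92 (122 − 37, 122 − 30) has that visit before month 4. On the Table 5-1 reading no scan is required after the last dose.

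**7. Size.** The documents give no rate of early stopping without progression for this trial. Let s be the assumed share. The 9% is borrowed from the renal-cell trial in 1.2.3.4; 5% and 20% bracket it and have no source. True PFS4 is 20%, and F without the problem is 0.365. Each cell shows the rate the count would read, then F at that rate.

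| How stoppers are handled | s = 5% | s = 9% | s = 20% |
|---|---|---|---|
| Excluded, all would have failed: 0.20/(1 − s) | 21.1%; 0.336 | 22.0%; 0.312 | 25.0%; 0.241 |
| Excluded, stoppers at 10%: (0.20 − 0.10s)/(1 − s) | 20.5%; 0.350 | 21.0%; 0.338 | 22.5%; 0.298 |
| Excluded, stoppers at the common rate | 20%; 0.365 | 20%; 0.365 | 20%; 0.365 |
| All counted as failures, common rate: 0.20(1 − s) | 19.0%; 0.395 | 18.2%; 0.419 | 16.0%; 0.492 |
| All counted as successes, common rate: 0.20(1 − s) + s | 24.0%; 0.263 | 27.2%; 0.199 | 36.0%; 0.085 |

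Expected early stoppers among 18 (18s): 0.9, 1.6 and 3.6. Chance of at least one, 1 − (1 − s)^18: 60%, 82% and 98%.

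**The case against.** The case for the plan is substantial, and several stronger readings do not survive it.

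- **A contradiction on scans.** A reader might infer that 5.5 contradicts Table 5-1 and 5.3. It does not clearly do so: 5.5 anchors the interval to drug start and is silent on scanning off drug. Read together, the passages can mean that scans end with drug. That leaves a gap in follow-up for an event-based endpoint, not two opposed instructions.
- **An open final denominator.** A reader might infer that the final count is equally unsettled. The 0.271 width needs all 18, and 2.5.1 provides no replacements. Both weigh against dropping patients at the end. What is missing there is the yes/no status of an early stopper.
- **A disabled futility rule by design.** The wording on completed treatment was most likely meant to say when each look happens. The documents do not show an intention to count finishers only. The text nevertheless allows it and offers no definition of evaluable to exclude it.
- **An automatic halt.** A reader might infer that any unknown status at the first look halts enrolment. Section 7.5 halts only when the required successes are missing, so one success among the other five is enough to go on.
- **Size.** The renal-cell 9% covers adverse-event stops over a median treatment of 7.6 months, so it is not a four-month rate. At 5–9% the shift is 1 to 2 percentage points even in the worst exclusion case. This objection stands.

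**Conclusion.** The point holds as a defect of definition plus a gap in follow-up. The wording of the looks does not match the endpoint, and nothing says how a patient who stops early without progression is classified at month 4. Neither statement depends on an assumed rate.

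The numerical effect does. At an assumed 5–9%, and with every stopper a hidden failure who is excluded, a true 20% reads 21.1–22.0% and futility stopping falls from 0.365 to 0.336–0.312. It is large only at the unsourced 20%. With stoppers at the common rate, exclusion adds no bias. The direction is not fixed: stops for toxicity or lost benefit may hide failures, while withdrawals of consent may not.

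The reason to act is that a single status can decide a look. If none of the other five patients at the first look is a success, an unknown sixth status also leaves the enrolment halt with no rule to end it.

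**What to change.** 1. In 7.4 and 7.5, define the looks as the first 6, 9, 12 and 15 treated patients in order of first dose, once each has reached four months from first dose or has progressed or died earlier. Fixing the order keeps early failures from entering ahead of patients still in follow-up. Use all treated patients as the final PFS4 denominator.
2. Reconcile Table 5-1, 5.3 and 5.5 so that patients who stop drug without progression keep the existing 8-weekly CT or MRI through week 16. State that this scan, with its window, decides month-4 progression status; deaths still count to four months, as 7.3 defines.
3. Count a patient with no status at that point, for example after consent withdrawal, as not achieving PFS4 in the primary count. State in advance how a patient who first starts other anticancer treatment is counted. Give a sensitivity analysis under the alternative.

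**Cost.** Wording in five places, and at most two scans (weeks 8 and 16) per early stopper: on average at most 2 × 0.9 = 1.8 scans in the trial at 5%, or 2 × 1.62 = 3.2 at 9%. Look sizes and Table 7-1 stay as they are. Remaining unknowns counted as failures lower the estimate slightly. If no stopper were scanned and stoppers had the common rate, a true 20% would read 19.0% at 5% or 18.2% at 9%, so the scans in step 2 matter more than the choice of rule in step 3.

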5.4 Laboratory Assessments

Laboratory panels are composed of the following:

Hematology	
• WBC count with differential (including at minimum: neutrophils, basophils, eosinophils, lymphocytes, monocytes)• hematocrit• platelet count• RBC count• hemoglobin	
Serum chemistry	
• albumin• ALP• ALT• AST• bicarbonate• BUN• chloride• creatinine• Glucose• calcium•	
• magnesium• phosphorus• potassium• sodium• total bilirubin• total protein
Urinalysis	
• appearance• color• pH• specific gravity• ketones• protein• UPCR• glucose• bilirubin• nitrite• creatinine• urobilinogen	
• occult blood (microscopic examination of sediment will be performed only if the results of the urinalysis dipstick evaluation are positive)
Other	
• TSH, Free T4• Pregnancy test (urine or serum) for women of child-bearing potential	
• PT/INR or PTT• 24 hour urine collection for protein^a• Adrenal hormones profile(ACTH, cortisol, aldosterone, plasma renin activity, DHEA-sulfate, testosterone in women, estradiol in men and postmenopausal women)• Mitotane level*

ALP, alkaline phosphatase; ALT, alanine aminotransferase; AST, aspartate aminotransferase; BUN, blood urea nitrogen; ESR, INR, International Normalized Ratio; PT, prothrombin time; PTT partial

Proprietary Information of MD Anderson

thromboplastin time; RBC, red blood cell; TSH, thyroid stimulating hormone; UPCR, urine protein/creatinine ratio; WBC, white blood cell.

*Only if prior mitotane use within 6 months.

^a Consider 24-hour urine collection for protein if UPCR>1 mg/mg

Abnormalities in clinical laboratory tests that lead to a change in subject management (eg, dose delayed [withheld] or reduced, requirement for additional medication, treatment or monitoring) are considered clinically significant for the purposes of this study, and will be recorded on the Adverse Events Case Report Form (CRF). If laboratory values constitute part of an event that meets criteria defining it as serious, the event (and associated laboratory values) must be reported as an SAE.

